5.4 Alternatives

At the time of study accrual, all patients will be offered access to standard six weeks radiotherapy, including 5 weeks of treatment to the whole breast or chest wall and regional lymph nodes using a standard 4-field plan, followed by a boost to the tumor bed or scar if required.

5.5 Compensation

No compensation is available for participating in the study.

6 SURGERY

Patients will have completed all breast cancer surgical procedures prior to accrual into this protocol in order to establish eligibility criteria. Final pathology margins must be at least 1 mm in all directions to be eligible. The patient may undergo re-excision if the initial margins are involved or close (< 1 mm). If the patient meets the eligibility criteria after re-excision, she may be entered onto the study. Patients must also undergo lymph node dissection of axillary levels

I/II with removal of at least 8 nodes.

7 RADIOTHERAPY SPECIFICATIONS

7.1 Treatment Planning using Hybrid IMRT Technique

In the context of a Phase I/II prospective study, this protocol will test whole breast and regional nodal radiotherapy using a hybrid approach. Patients will receive whole breast radiotherapy in a prone position with a concomitant daily boost to the tumor bed over three weeks, a technique which has previously been evaluated in over 500 patients (NYU 03-30 and NYU 05-181) and has shown excellent tolerance and results. In addition, an intensity modulated radiation therapy (IMRT) technique will be used to deliver concomitant radiotherapy to axillary level III and supraclavicular lymph nodes. In patient Cohort A, axillary levels I and II will also be part of the radiation target. Patients status post mastectomy will receive whole reconstructed breast/chest wall radiotherapy and nodal irradiation. A concomitant boost to the scar region will be offered only to patients without reconstruction.

7.2 Dose Specification

Patients will receive 15 daily radiation fractions of 2.7 Gy, Monday to Friday for three weeks, to the entire breast/chest wall and axillary level III and supraclavicular nodes with a daily concomitant boost of 0.5 Gy to the tumor bed, for a total daily dose of 3.2 Gy to the tumor bed (2.7 Gy + 0.5 Gy). The overall dose will be 40.5 Gy to the breast/chest wall, axillary level III and supraclavicular nodes, and 48.0 Gy to the tumor bed.

7.3 CT Simulation

All patients will be CT scanned in the prone position on a specially designed board that allows the indexed breast tissue to fall freely below the board, granting unobstructed access to the breast through radiation ports from multiple beam angles. CT slice thickness should be 3.75 mm or less. Prior to the patient lying prone on the table for scanning, the borders of the breast/chest wall fields will be marked with radio-opaque CT fiducial markers. These markers will be used to outline the breast/chest wall treatment volume according to conventional treatment guidelines. Borders of the fields will be set medially at mid-sternum, laterally at the anterior edge of latissimus dorsi, superiorly at the bottom of the clavicular heads and inferiorly 2 cm from the infra-mammary fold. Patients will be tattooed with leveling marks for setup alignment with room lasers and for positioning the isocenter of the beams. A tattoo will be placed on the lateral breast tissue as a landmark for planning and positioning. Patients status post mastectomy will also be simulated prone with similar field borders. In addition, the chest wall scar will carefully be marked with radio-opaque CT fiducial markers.

Contouring of breast tumor bed, axillary level III nodes, supraclavicular nodes, indexed and contralateral breast tissue, ipsilateral brachial plexus, esophagus, heart, right and left lung, spinal cord, spinal cord plus 5 mm margin and right and left lobes of the thyroid will be

performed in order to guide beam arrangement and optimal normal tissue avoidance. In patients who have undergone pre-operative breast MRI, the breast glandular tissue will be contoured with the help of a radiologist co-investigator (Drs. [name] and [name]), to better inform the design of the treatment fields.

The patient will be CT scanned and treated in the supine position if the patient cannot lie prone, or if the prone plan fails to satisfy the dose constraints specified in Section 7.5.6

7.4 Target Delineation

- 7.4.1 The physician designs tangent fields to encompass the whole breast. The PTVBreast is created from the 50% isodose line associated with the tangent fields. Technically this is accomplished by converting the 50% isodose level to a structure, smoothing and then removing parts extending outside the 50% isodose structure with an additional 0.6 cm margin. The PTVBreast volume overlapping the heart and lung is excluded.
- 7.4.2 PTVTumor is the tumor bed, as identified on CT with an additional 1.0 cm 3D margin. Post-mastectomy PTVTumor is the tumor bed and depending on clinical judgement may or may not include the scar.
- 7.4.3 PTVTumor Eval is the PTVTumor cropped 0.6 cm from the skin.
- 7.4.3 PTVNodes includes axillary level III and supraclavicular lymph nodal regions as identified on CT with an additional 0.5 cm 3D margin. For patients in Cohort A PTVNodes will include axillary levels I-III and supraclavicular nodal regions as identified on CT with an additional 0.5 cm 3D margin. However, the PTV will not be expanded medially to better spare the esophagus.
- 7.4.4 PTVNodesEval is the PTVNodes cropped 0.6 cm from the skin.

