7.5.6 Dose Constraints

The dose constraints below represent acceptance criteria for the resulting dose distribution.

1. Target volume dose constraints:
 - PTVTumor: $V \geq 98\%$
 - PTVBreast: $V \geq 95\%$
 - PTVNodesEval: $V \geq 95\%$
2. Normal tissue dose constraints:
 - a. Heart: $V < 5\%$
 - b. Ipsilateral lung: $V < 20\%$
 - c. Contralateral lung: $V < 15\%$
 - d. Spinal cord: 37.5 Gy maximum
 - e. Spinal cord plus 0.5 cm margin: 40 Gy maximum
 - f. Thyroid: contralateral lobe 15 Gy maximum
 - g. Esophagus: $V < 50\%$, 40.5 Gy maximum
 - h. Ipsilateral brachial plexus: 42 Gy maximum
 - i. Contralateral breast: Efforts should be made to keep the contralateral breast completely outside the primary beams

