14.3.1 Primary Endpoints

The primary outcome of this study is the proportion of patients with acute toxicity greater than grade 2 (Skin toxicities grade 3 and above) occurring within 60 days after first day of treatment. This rate will be estimated with an exact 95% confidence interval. Treatment feasibility will be evaluated for each patient by the ability to meet all physics dose constraints as outlined in section 7.5.6. The proportion of patients who meet the constraints will be estimated with an exact 95% confidence interval.

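### The feasibility endpoint scores the tumor bed on uncropped PTVTumor while the skin-cropped PTVTumor Eval is defined and never used, so a superficial bed can count as not feasible

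*Combined protocol and SAP*

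**What the plan says.** - **Target volumes (7.4).** "PTVTumor is the tumor bed, as identified on CT with an additional 1.0 cm 3D margin"; no limit at the skin is stated. The first of two items numbered 7.4.3 adds: "PTVTumor Eval is the PTVTumor cropped 0.6 cm from the skin". The nodal counterpart is built the same way: "PTVNodesEval is the PTVNodes cropped 0.6 cm from the skin".
- **Plan criteria (7.5.6).** The tumor-bed line names PTVTumor, with V at least 98%. The nodal line names PTVNodesEval, with V at least 95%. PTVTumor Eval does not appear there or anywhere else.
- **Feasibility endpoint (14.3.1).** Each patient is classified by the "ability to meet all physics dose constraints as outlined in section 7.5.6", and the proportion is reported with an exact 95% confidence interval.
- **Supine trigger.** Section 7.3 moves a patient to supine scanning and treatment if she cannot lie prone or "if the prone plan fails to satisfy the dose constraints specified in Section 7.5.6". Section 2.3 restricts the additional supine set-up to listed heart and lung limits.
- **Boost.** Under 7.1, after mastectomy, "A concomitant boost to the scar region will be offered only to patients without reconstruction". Sections 7.2 and 7.5.6 state the tumor-bed dose and criterion without exception.
- **Superficial targets (7.5.4).** Flash of 1 cm is added when PTVTumor is within 1 cm of the body surface, and electrons are permitted.

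**The concern.** Defining a cropped evaluation structure and then scoring the uncropped one suggests that one of the two sections was not updated. The nodes are scored on their cropped volume, so the two targets are treated differently with no reason given.

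This matters statistically because 14.3.1 is an all-or-nothing rule: one missed item makes the patient not feasible. PTVTumor extends 1.0 cm beyond the bed in every direction. For a shallow bed, part of it lies in the superficial rim or in air. A primary proportion can then partly reflect bed depth, and a reader could not separate those failures from failures of nodal coverage or organ sparing. Under 7.3 the same failures can also enter the re-simulation count, a secondary objective (1.2.1).

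A related gap needs no geometry. For a reconstructed mastectomy patient with no scar boost, the plan does not say whether the tumor-bed item belongs to the full set of constraints, so two analysts could classify her differently.

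**Working it through.** **1. The plan's own figure.** Section 14.5 states that with 104 patients and an observed feasible proportion of at least 0.95, the exact lower 95% limit is at least 0.89. The smallest whole count reaching 0.95 is 99/104 = 0.952. The exact (Clopper-Pearson) lower limit is the 0.025 quantile of Beta(99, 6), which is 0.891. The figure reproduces and does not depend on which structure is scored.

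**2. Share of PTVTumor near or beyond the skin.** From the documents: margin 1.0 cm, crop 0.6 cm, allowed miss 100% − 98% = 2%. Assumed: a spherical bed of radius r, flat skin, and no clipping to the body. Let d be the distance from bed surface to skin and R = r + 1.0. The spherical-cap share is

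f = h²(3R − h) / (4R³),

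with h = 1.6 − d for rim plus air, and h = 1.0 − d for air alone.

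For r = 1.5 (R = 2.5, 4R³ = 62.5):
- d = 1.0, h = 0.6: 0.36 × 6.9 / 62.5 = 4.0%
- d = 0.75, h = 0.85: 0.7225 × 6.65 / 62.5 = 7.7%
- d = 0.5, h = 1.1: 1.21 × 6.4 / 62.5 = 12.4%
- air alone at d = 0.5, h = 0.5: 0.25 × 7.0 / 62.5 = 2.8%

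The same formula for other bed sizes:

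| Bed radius (cm) | Rim plus air, d = 1.0 | Rim plus air, d = 0.5 | Air alone, d = 0.5 |
|---|---|---|---|
| 1.0 | 6.1% | 18.5% | 4.3% |
| 1.5 | 4.0% | 12.4% | 2.8% |
| 2.0 | 2.8% | 8.9% | 1.97% |
| 2.5 | 2.1% | 6.6% | 1.5% |

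Setting f = 2% and solving for d, rim plus air uses up the allowance at depths of about 1.26 cm (radius 1.0) to 1.01 cm (radius 2.5). Air alone does so at about 0.66 to 0.41 cm.

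**3. Effect on the proportion.** The documents do not give the share g of patients who would fail for this reason alone, so g is an assumption, as is an underlying feasibility of 0.95. With independent failures, p = 0.95 × (1 − g).

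| g | p | Expected count of 104 (rounded) | Exact lower limit at that count | P(at least 99 of 104) |
|---|---|---|---|---|
| 0% | 0.950 | 99 | 0.891 | 0.58 |
| 2% | 0.931 | 97 | 0.866 | 0.27 |
| 5% | 0.9025 | 94 | 0.830 | 0.05 |
| 10% | 0.855 | 89 | 0.773 | 0.001 |

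**The case against.** The strongest reply is that no section says shallow beds fail. A reader might infer from the geometry that they do, but the documents do not support that.

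- **Dose level.** The dose level after V is missing from the text available to me. That is not a fault of the plan, but without it one cannot say whether tissue in the rim would fall short.
- **Technique.** Section 7.5.4 anticipates superficial targets with flash and electrons. Flash adds no dose to volume in air, but the choice of modality can affect superficial coverage.
- **Clipping.** Whether PTVTumor is clipped to the body contour is not stated. Even unclipped, air alone does not always defeat the 98% criterion: at 0.5 cm depth it takes 1.97% for a 2.0 cm bed, just inside the allowance.

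A reader might also infer that tumor-bed coverage is foreign to the objective, or that supine positioning cannot help. Neither is supported. Objective 1.1.1 covers breast and nodes, and 7.1 and 7.5.5 put breast, boost and nodes in one regimen and plan, so tumor-bed coverage is a legitimate part of feasibility. Nothing in the documents shows that bed-to-skin geometry is the same prone and supine.

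It is also fair that 14.5 sets no pass mark for feasibility, only a precision statement, and that not applicable is a natural reading where no boost is planned. That reading is not written down, however. The mismatch between 7.4 and 7.5.6 stands, as does its route into a primary endpoint. A lost suffix on the tumor-bed line is possible but unlikely, because Eval survives on the nodal line of the same list.

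**Conclusion.** The inconsistency is real and lies in the rule that defines a primary endpoint. A superficial tumor bed can make a patient not feasible; the documents do not show that it will. Under the stated assumptions (spherical bed, flat skin, no clipping), the share of PTVTumor in the 0.6 cm rim or beyond the skin is 2.1% to 6.1% at 1.0 cm depth and 6.6% to 18.5% at 0.5 cm, for bed radii of 2.5 down to 1.0 cm, against a 2% allowance. The effect on the reported proportion depends on an unknown frequency: if 2% to 5% of patients failed for this reason alone, about 97 to 94 of 104 would be expected feasible instead of 99.

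It would go too far to conclude that the re-simulation count is distorted. That follows from 7.3 but not from 2.3, and the two must be reconciled. No stated sample size, alpha, power or precision figure is wrong. This review takes no position on which structure should govern plan acceptance.

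**What to change.** 1. Reconcile 7.4.3 with 7.5.6 so that one tumor-bed structure is named for the feasibility endpoint. It should be the one the investigators choose for plan acceptance; otherwise a rejected plan could be counted as feasible, or the reverse. State whether PTVTumor is clipped to the body.
2. Report the feasibility proportion, with its exact interval, under both PTVTumor and PTVTumor Eval.
3. Tabulate failures by constraint: tumor bed, breast, nodes and each organ.
4. State in 14.3.1 that the tumor-bed item is not applicable when no boost is planned under 7.1.
5. Reconcile the supine triggers in 2.3 (heart and lung limits) and 7.3 (any 7.5.6 constraint), and count re-simulations by reason.
6. Correct the duplicate number 7.4.3.

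The cost is protocol wording and a few extra table rows. The cropped structure is already defined, and its coverage can be read from the same dose-volume histogram. The sample size is unaffected.

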7.5 Technical Factors

- 7.5.1 Dose calculations will include heterogeneity corrections.
- 7.5.2 Whole Breast fields – 3D tangents plus IMRT tangents
 1. The prone position requires careful placement of the isocenter during planning to avoid collision between the gantry and the breast board, couch, or patient.
 2. 3D tangents deliver nominally 67% of the whole breast dose, using 6 MV photons and including 2-3 cm flash. The fields are wedged and weighted to obtain a uniform dose distribution, normalized to allow approximately 105% maximum dose. 16 MV photons may be used for patients with large separations to reduce magnitude of dose maximum.
 3. IMRT tangents deliver nominally 33% of the whole breast dose, using 6 MV photons and including 2-3 cm flash. The 3D tangents are used as a base for optimization.

7.5.3 Axillary level I-III and supraclavicular nodes (PTVNodes)
1. Three or more IMRT fields.

7.5.4 PTVTumor fields
1. Non-coplanar beam arrangement is encouraged, but not required.
2. Integrated boost within the IMRT tangents is allowed.
3. Electron therapy may be utilized.
4. No photon beam will be directed toward heart, lung, contralateral breast, or thyroid
5. Inclusion of soft tissue not irradiated by the whole breast tangents is allowed to aid in target coverage.
6. If the PTVTumor, as visualized in the beams-eye-view (BEV), is within 1 cm of the body surface, 1 cm of flash will be added to the field(s), painting fluence for IMRT fields.

7.5.5 IMRT Optimization

IMRT optimization is performed either by using the 3D tangents plan as a base plan for all IMRT fields, or by using a plan with all tangent fields (IMRT and 3D) as a base for the IMRT nodal fields. Regardless, a single plan is created with 3D breast tangent fields, IMRT breast tangent fields, boost fields if used, and IMRT axillary level III and supraclavicular nodal fields.

7.5.6 Dose Constraints

The dose constraints below represent acceptance criteria for the resulting dose distribution.

1. Target volume dose constraints:
 - PTVTumor: $V \geq 98\%$
 - PTVBreast: $V \geq 95\%$
 - PTVNodesEval: $V \geq 95\%$
2. Normal tissue dose constraints:
 - a. Heart: $V < 5\%$
 - b. Ipsilateral lung: $V < 20\%$
 - c. Contralateral lung: $V < 15\%$
 - d. Spinal cord: 37.5 Gy maximum
 - e. Spinal cord plus 0.5 cm margin: 40 Gy maximum
 - f. Thyroid: contralateral lobe 15 Gy maximum
 - g. Esophagus: $V < 50\%$, 40.5 Gy maximum
 - h. Ipsilateral brachial plexus: 42 Gy maximum
 - i. Contralateral breast: Efforts should be made to keep the contralateral breast completely outside the primary beams

7.6 Portal Imaging

Portal images of orthogonal setup fields will be acquired on days 1, 2, and 3 then weekly thereafter. In addition, portal images will be acquired of each treatment field (except where geometrically impractical) during the first three days of treatment.

Cone beam CT (CBCT) of the nodal region will be acquired once on a day when orthogonal setup fields are imaged. No alignment adjustment will be made based on the CBCT.

8 DOSE MODIFICATIONS AND STOPPING CRITERIA

8.1 Dose Modification

In case of grade 3 acute skin toxicity occurring during the course of the 3-week treatment, the dose per fraction of the remaining treatment fractions will be reduced to 2 Gy/fraction until completion.

8.2 Stopping Criteria

Regional nodal recurrences occur in 1 - 5% of patients with early stage breast cancer who have undergone mastectomy or breast conserving therapy (Fisher, Anderson et al. 2002; Moran and Haffty 2002; Harris, Hwang et al. 2003). While most nodal recurrences occur within the first five years after treatment, nodal recurrences have been documented for more than twenty years after completion of treatment (Lukens, Vapiwala et al. 2009).

Based on this data, a stopping rule for regional node recurrences will be implemented with an evaluation after every 21 patients are observed for at least 1 year post treatment. The schema is described in Section 14. This rule allows early stopping based on an excess of incidence of regional node recurrences (greater than 5% of patients).

9 ADVERSE EVENTS: LIST AND REPORTING REQUIREMENTS

9.1 Adverse Events and Potential Risks List

Expected toxicities include fatigue and skin reactions within the radiation field. Erythema, dry and moist desquamation of the skin will be recorded weekly. Breast edema and tenderness are additional possible acute side effects. Acute (\leq 60 days after first day of treatment) and late toxicity ($>$ 60 days after first day of treatment) will be reported as scheduled in the study calendar. This study will utilize the descriptions and grading scales as described in *Common Terminology Criteria for Adverse Events v3.0 (CTCAE)* for acute toxicity and in the LENT/SOMA classification for late toxicities (appendix 1). Toxicities will be tracked using the Toxicity Tracking Form (appendix 2).

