1. OBJECTIVES

- 1.1 Primary Objectives
 - 1.1.1 To evaluate feasibility of prone IMRT to breast, level III and supraclavicular nodes (physics and dosimetry parameters)
 - 1.1.2 To estimate acute toxicity of prone IMRT to breast, level III and supraclavicular nodes
- 1.2 Secondary Objectives
 - 1.2.1 To estimate the incidence of re-simulation to improve dosimetry after initial prone set-up
 - 1.2.2 To evaluate changes in QOL of patients assessed at baseline and after treatment
 - 1.2.3 To estimate incidence of late radiation toxicity (e.g., lymphedema, fibrosis and telangiectasia) and to examine genetic determinants of breast fibrosis
- 1.3 Exploratory Objectives
 - 1.3.1 To estimate local recurrence rates
 - 1.3.2 To estimate median Disease Free Survival (DFS)
 - 1.3.3 To estimate median Time to Progression
 - 1.3.4 To estimate median Overall Survival (OS)
- 1.4 Cohort A Objectives
 - 1.4.1 To explore feasibility of treating in the prone position a comprehensive nodal volume, that includes axillary nodal levels I and II in addition to the fields already treated per this protocol (i.e., axillary nodal levels III, supraclavicular fossa and breast or chest wall tangents, depending on whether the patient has undergone segmental mastectomy or mastectomy, respectively)

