2.5 Late Radiation Effects and Assessment of Risk

For patients who require regional nodal irradiation, an accelerated regimen of three weeks is very appealing, but in the past it has generally been discouraged because of concerns regarding the morbidity of larger doses to normal tissue, including lymphedema and brachial plexus

injury. The current protocol is likely to overcome some concerns of lymphedema by avoiding irradiation of the axillary stations where a surgical dissection was performed. Nevertheless, a field that includes axillary level III and the supraclavicular nodes will also include most of the ipsilateral brachial plexus, warranting cautious radiobiological modeling of late effects of radiotherapy to this target.

The severity of late effects is known to be dependent on both total dose and fraction size. In the linear-quadratic model, sensitivity to fraction size is expressed by the alpha/beta ratio, with a lower ratio indicating increased sensitivity. In a recent review, Kurtz summarized known alpha/beta values for tissues irradiated in breast cancer treatment (Table 4) (Kurtz 2005).

Table 4 - A Review of Results Summarized by Kurtz et al.

End-point	Author (reference)	Alpha/beta (Gy)
Telangiectasia	Turesson et al. [14]	4.2
Chest wall fibrosis	Bentzen et al. [6]	1.9
Shoulder stiffness	Bentzen et al. [5]	3.5
Brachial plexus injury	Powell et al. [12]	1.5-2.0
Rib fractures	Overgaard [11]	1.8-2.8
Breast cosmesis (fibrosis)	Van Limbergen et al. [16]	2.5

Due to low alpha/beta ratios for most of these tissues, it is possible that higher rates of late complications could be observed with an accelerated regimen. To clinically evaluate the impact of hypofractionation on brachial plexus injury, Powell et al. reported their experience with an accelerated schedule in a seminal paper published in 1990, describing the late effects of a group of 449 patients irradiated to the breast and regional lymph nodes with mean brachial plexus dose 45.9 Gy in 15 fractions (3 Gy per fraction) versus 54 Gy in 30 fractions (1.8 Gy per fraction) (Powell, Cooke et al. 1990). He noted a cumulative actuarial incidence of radiation-induced brachial plexus injury at 5.5 years of 5.9% versus 1.0% for the large and small fraction size group, respectively. It is important to note that the dose was higher than our proposed dose of 40.50 Gy given in 2.7 Gy daily fractions and that the fields included the entire axilla.

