APPENDIX 1 – COMMON TOXICITY CRITERIA

Acute Toxicity from *Common Terminology Criteria for Adverse Events v3.0 (CTCAE)*, Published: August 9, 2006

	Grade 0	Grade 1	Grade 2	Grade 3	Grade 4
FATIGUE	No change	Mild fatigue over baseline	Moderate or causing difficulty performing some ADL	Severe fatigue interfering with ADL	Disabling
RADIATION DERMATITIS	No change	Faint erythema or dry desquamation	Moderate to brisk erythema; patchy moist desquamation, mostly confined to skin folds and creases; moderate edema	Moist desquamation other than skin folds and creases; bleeding induced by minor trauma or abrasion	Skin necrosis or ulceration of full thickness dermis; spontaneous bleeding from involved site
PAIN	No pain	Mild pain not interfering with function	Moderate pain; pain or analgesics interfering with function, but not interfering with ADL	Severe pain; pain or analgesics severely interfering with ADL	Disabling

Table 1. RTOG/EORTC and LENT/SOMA classification of late effects

RTOG/EORTC	Grade 1	Grade 2	Grade 3	Grade 4
Skin	Slight atrophy, pigmentation change, some hair loss	Patchy atrophy, moderate telangiectasia, total hair loss	Marked atrophy, gross telangiectasia	Ulceration
Subcutaneous tissue	Slight induration (fibrosis), and loss of subcutaneous fat	Moderate fibrosis, but asymptomatic; slight field contracture, $\leq 10\%$ linear reduction	Severe induration and loss of subcutaneous tissue, field contracture, $\geq 10\%$ linear reduction	Necrosis
LENT/SOMA				
Breast				
Subjective				
Pain	Occasional and minimal Hypersensation, pruritus	Intermittent and tolerable	Persistent and intense	Refractory and excruciating
Objective				
Telangiectasia	$<1\text{ cm}^2$	$1\text{--}4\text{ cm}^2$	$>4\text{ cm}^2$	
Fibrosis	Barely palpable, increased density	Definite increased intensity and firmness	Very marked density, retraction, and fixation	
Edema	Asymptomatic	Symptomatic	Secondary dysfunction	
Retraction, atrophy	10–25%	$>25\text{--}40\%$	$>40\text{--}75\%$	Whole breast
Ulcer	Epidermal only, $<1\text{ cm}^2$	Dermal only, $>1\text{ cm}^2$	Subcutaneous	Bone exposed, necrosis
Lymphedema, arm circumference	2–4-cm increase	$>4\text{--}6\text{-cm}$ increase	$>6\text{-cm}$ increase	Useless arm
Skin				
Pigmentation change	Transitory, slight	Permanent, marked	—	—

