APPENDIX 2 – TOXICITY TRACKING FORM

Department of Radiation Oncology
NYU Hospitals Center
[name]
New York, NY 10016

PHYSICIAN'S PROGRESS NOTE

Fraction: 1-5 6-10 11-15 45-60 day F/U

The following critical elements of the patient's weekly exam have been covered:

- Chart & Dosimetry, Treatment set up & positioning review*
- Port Film or image review*
- Examination of patient for evaluation and progress of treatment (see notes below)*

Progress note: _____

Please indicate Toxicity due to Radiation Treatment on the following chart:

	Grade 0	Grade 1	Grade 2	Grade 3	Grade 4
FATIGUE					
	No change	Mild fatigue over baseline	Moderate or causing difficulty performing some ADL	Severe fatigue interfering with ADL	Disabling
RADIATION DERMATITIS					
	No change	Faint erythema or dry desquamation	Moderate to brisk erythema; patchy moist desquamation, mostly confined to skin folds and creases; moderate edema	Moist desquamation other than skin folds and creases; bleeding induced by minor trauma or abrasion	Skin necrosis or ulceration of full thickness dermis; spontaneous bleeding from involved site
PAIN (Breast)					
	No pain	Mild pain not interfering with function	Moderate pain; pain or analgesics interfering with function, but not interfering with ADL	Severe pain; pain or analgesics severely interfering with ADL	Disabling

Attending Signature: _____ Date: _____

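### No scheduled, clinician-graded item covers brachial plexopathy, esophagitis/dysphagia or pneumonitis, although the protocol names or dose-constrains all three organs

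*Combined protocol and SAP*

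**What the plan says.** Primary objective 1.1.2 is "To estimate acute toxicity of prone IMRT to breast, level III and supraclavicular nodes", and the synopsis hypothesis is that the three-week nodal regimen is feasible and well tolerated. Section 2.5 gives lymphedema and brachial plexus injury as the reasons accelerated nodal schedules have been discouraged, and adds: "Nevertheless, a field that includes axillary level III and the supraclavicular nodes will also include most of the ipsilateral brachial plexus". Section 7.5.6 sets acceptance limits that include "Ipsilateral brachial plexus: 42 Gy maximum", with further limits for esophagus, both lungs and spinal cord. Section 7.4 withholds the medial nodal margin to spare the esophagus.

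For measurement, section 9.1 names CTCAE v3.0 for acute toxicity and grades late effects "in the LENT/SOMA classification for late toxicities (appendix 1). Toxicities will be tracked using the Toxicity Tracking Form (appendix 2"). The Appendix 2 form tells the physician: "Please indicate Toxicity due to Radiation Treatment on the following chart". That chart has three rows: fatigue, radiation dermatitis and breast pain. Its time points are "Fraction: 1-5 6-10 11-15 45-60 day F/U". The late criteria in Appendix 1 are headed "Table 1. RTOG/EORTC and LENT/SOMA classification of late effects".

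**The concern.** The new element in this trial is the hypofractionated nodal field in the prone position. A claim that it is well tolerated needs evidence on the organs in or beside that field, and the protocol itself names them. If nobody is asked to score an organ at a set visit, the absence of a report may mean no event or no question. The toxicity tables would then be informative about skin, breast, arm circumference and thyroid, but silent on plexus and esophagus, and readers could take that silence as a favourable result. The monitoring committee, which reviews safety at least yearly under section 13.1, would have the same difficulty.

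**Working it through.** The plan states no figure for this point, so the main check sets each organ against each source of data.

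| Organ | Why the protocol cares | Scheduled clinician-graded item | Other routes |
|---|---|---|---|
| Arm (lymphedema) | 2.5 | Yes: circumference at baseline, end of treatment and yearly (2.8.2, calendar) | Quality-of-life (QOL) items |
| Thyroid | 2.8.1, 7.5.6 | Direct test: TSH and T4 at baseline and yearly | None needed |
| Brachial plexus | 2.5, Table 5, 7.5.6 | None | Event reports, free text, non-specific QOL arm and shoulder items to 2 years |
| Lung | 2.6.1, 7.5.6 | None | Event reports, free text, QOL cough and breathing items to 2 years |
| Esophagus | 7.4, 7.5.6 | None | Event reports, free text only |

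Lymphedema and plexus injury are named together in section 2.5, but only lymphedema has a scheduled measurement. The QOL forms (Appendix 3) ask about arm pain, arm and shoulder movement, shoulder stiffness and lifting. They do not ask about arm weakness, arm or hand numbness, or swallowing. They are given at baseline, the last week of treatment, day 45-60 and 2 years, and the follow-up form excuses patients after a recurrence or second primary. Clinical follow-up runs yearly to 5 years (section 5.3), so years 3 to 5 have no patient-reported item either.

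**Check of the biologically effective dose (BED) given for the plexus.** Formula from section 2.6: BED = nd(1 + d/(α/β)), with α/β = 2 for the plexus (Table 5).
- This trial: 40.5 × (1 + 2.7/2) = 95.2, which reproduces the 95 in Table 5.
- Large-fraction group of the series cited in 2.5 (45.9 Gy in 15 fractions, 3.06 Gy each): 45.9 × (1 + 3.06/2) = 116.1.
- Small-fraction group (54 Gy in 30): 54 × (1 + 1.8/2) = 102.6.
- At α/β = 1.5, the lower value in Table 4, the three are 40.5 × 2.8 = 113.4, 45.9 × 3.04 = 139.5 and 54 × 2.2 = 118.8.

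At the prescribed dose this regimen therefore sits below both cited groups.

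**What scheduled scoring would provide.** With no case among n patients actively assessed, the exact two-sided 95% upper limit is 1 − 0.025^(1/n).
- n = 104 (section 14.5): 1 − 0.025^(1/104) = 0.0348, or 3.5%.
- The documents give no loss to follow-up. If 80 were assessed, the limit is 1 − 0.025^(1/80) = 4.5%; if 60, 1 − 0.025^(1/60) = 6.0%.

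Each limit requires that every patient in n was asked. Under the plan as written, n is unknown for the plexus, esophagus and lung.

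**The case against.** The strongest reply is that the trial has several ways to learn of such events. Section 9.3 sends all adverse events to an event form without limiting the organ. Section 9.2 routes serious events, graded by CTCAE v3.0, to the monitoring committee. The Appendix 2 form has a free-text note and a weekly examination item. The QOL forms score cough, breathing, shoulder stiffness and arm function, and end with an open question on other problems. Section 9.1 invokes CTCAE v3.0 and LENT/SOMA as such, and what the full scales contain cannot be judged from these documents. Dose to the three organs also enters the feasibility outcome in 14.3.1, and the primary toxicity endpoint is skin alone.

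Much of this stands. A reader might infer that the trial cannot report these toxicities, that its instruments cover only the breast, or that a plexus injury would have nowhere to be recorded. The documents contradict all three: the routes above exist, lymphedema and thyroid function are measured directly, and shoulder stiffness is scored by patients.

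A reader might also multiply the 5.9% injury rate cited in 2.5 by 104 to project cases here. That is not supported. The protocol notes that the cited series used a higher dose and treated the whole axilla, and the BED check agrees on dose. Cohort A, which adds levels I and II, weakens only the second point. The cited rate is also at 5.5 years, beyond the 5-year follow-up.

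Nor can one infer that adding the items would settle whether the rate is below 5.9%. The upper limits for 0 and 1 case in 104 (3.5% and 5.2%) exclude it, but the limit for 2 cases is 6.8%. Even at a true rate of 1.0%, the chance of at most one case is 1 − 0.279 = 0.72.

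None of this supplies scheduled, graded ascertainment with a known denominator.

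**Conclusion.** The gap is real but limited. Appendix 1 as printed, Appendix 2 and the study calendar contain no scheduled clinician-graded item for brachial plexopathy, esophagitis/dysphagia or pneumonitis. Cases may surface through other routes, but their incidence cannot be estimated with a valid denominator. The plexus is the most serious omission, because its injury is late and no form asks about it specifically. The esophagus has no item on any form. Lung symptoms are partly covered by patient report to 2 years.

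The 3.5% limit indicates scale only. It assumes that all 104 patients are actively assessed and followed to 5 years. The primary skin endpoint, sample size and stopping boundaries do not depend on this point. It is an inexpensive improvement that should be made, and the trial's main analyses stand without it.

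**What to change.** Add graded rows for esophagitis/dysphagia and cough/pneumonitis to the Appendix 2 form, completed weekly and at day 45-60, and print their grade definitions in Appendix 1. Add graded items for brachial plexopathy (arm and hand, motor and sensory) and pneumonitis to the yearly late-effects assessment, with a pre-treatment score so that surgical or chemotherapy effects can be separated. List these in the study calendar. In section 14.3, report the worst grade of each with the number assessed and an exact 95% confidence interval.

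The cost is an amendment to the protocol wording and forms, plus a few questions and a brief arm examination at visits already scheduled. The forms become slightly longer, and the toxicity table may look less favourable than it would without the questions.
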